13.5.3 The second part of the primary objective

The second part of the primary objective states that at least 98% of the n = 240 results must fall within ± 15 mg/dL(± 0.83 mmol/L) of the comparator result (comparator < 75 mg/dL/4.16 mmol/L)) or $\pm 20\%$ of the comparator result (comparator ≥ 75 mg/dL/4.16 mmol/L). Thus, with n = 240, there must be at least 236 BGMS results satisfying this requirement. This is equivalent to testing the hypotheses:

*H*₀: $Prob\{accurate\} < 98.33\%$ versus the alternative:

 H_1 : $Prob{accurate} \ge 98.33\%$

There is approximately a 95% chance of rejecting H_0 in favor of H_1 if the actual probability that a meter measurement would satisfy the ± 15 mg/dL or 20% is 98.33%. Conversely, there is about a 95% chance that the null will NOT be rejected if the actual probability that a result with the evaluation device would satisfy this definition of accuracy is only about 96.23%. It is possible

Protocol /CIP: GCA-PRO-2021-003-01 - Amendment 1 Ascensia Diabetes Care CONFIDENTIAL

that the sample size after the study is completed may not be exactly 240. The critical values will be approximately 95% or 98% of results (first and second parts of primary objective, respectively), and the associated hypotheses will be adjusted to reflect the change while maintaining no more than a 95% chance of rejecting the null hypotheses.

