8.0 Clinical Study Design

- 8.1 This is an open label, prospective, single arm study. The results of the study devices will be compared to the laboratory analyzer results from the same blood sample.
- For each BGMS, 120 evaluable samples (N=240 evaluable results due to duplicate testing) 8.2 are required. Therefore at least 120 subjects will be enrolled. Up to 200 subjects may be enrolled to obtain the required number of samples.

Protocol /CIP: GCA-PRO-2021-003-01 - Amendment 1 Ascensia Diabetes Care

Version: 14Oct2022 CONFIDENTIAL

8.3 Randomization:

- 8.3.1 Since two BGMSs will be tested in the study, the order of testing the study devices will be randomized.
- 8.3.2 Three strip lots (per BGMS) will be tested, with each sample tested with one lot. The strip lots will be randomized.
- **8.4** The results from these two BGMSs will not be compared to each other.
- **8.5** The study design follows CLSI- POCT12-A3:2013 and ISO 20916:2019(E) to ensure it is scientifically robust and valid.
- 8.6 Subjects with non-evaluable data will be replaced as needed to obtain N=120 samples, and N= 240 results (duplicate results) for each BGMS.

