13.0 Statistical Plan

13.1 Sample Size

- 13.1.1 The sample size requirement is based on the primary objective, section 7.0.
- 13.1.2 There will be a minimum of N = 120 study samples entered into the study. The meter results will be taken in duplicate, so that the total sample size of meter results will be at least 2*120 = 240.
- 13.1.3 With a sample size of n = 240 results, there is approximately a 95% chance that at least 228 of those results (95% of 240) will be "accurate" (errors within either ± 12 mg/dL (± 0.67 mmol/L) when the comparator result is < 100 mg/dL (5.55 mmol/L), or $\pm 12.5\%$ when the comparator result is ≥ 100 mg/dL (5.55 mmol/L) if the evaluation (meter) system has a 96.77% chance of yielding an "accurate" result.
- 13.1.4 Conversely, there is about a 95% chance of obtaining fewer than 228 "accurate" results if the system only has an approximately 92.03% chance of yielding an accurate result.
- 13.1.5 Note that each glucose result obtained with the evaluation devices will be considered either 'accurate' or 'not accurate', where accuracy depends on the particular test criterion as described in section 7.0 of this protocol.

Protocol /CIP: GCA-PRO-2021-003-01 - Amendment 1 Version: 14Oct2022

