13.5 Accuracy Analyses

13.5.1 Two sets of metrics will be calculated:

Relative (Percent) Difference (RD) for reference result \geq threshold glucose:

$$RD = \frac{M-C}{C} 100\%$$

where: M = strip/meter result and C = comparator or reference method result.

Difference (D) for reference result < threshold glucose:

$$D = M - C$$

Protocol /CIP: GCA-PRO-2021-003-01 - Amendment 1 Version: 14Oct2022

13.5.2 Primary objective:

The threshold glucose value is 100 mg/dL (5.55 mmol/L). Accuracy will be assessed using the CLSI. *Point-of-Care Blood Glucose Testing in Acute and Chronic Care Facilities; Approved Guideline – Third Edition*. CLSI document POCT12-A3. Wayne, PA: Clinical and Laboratory Standards Institute; 2013.

i.e., D within $\pm 12 \text{ mg/dL} (\pm 0.67 \text{ mmol/L})$ for comparator result < 100 mg/dL (5.55 mmol/L) and RD within $\pm 12.5\%$ for comparator result $\ge 100 \text{ mg/dL} (5.55 \text{ mmol/L})$.

For RD, the percent of results within $\pm 5\%$, $\pm 10\%$, $\pm 12.5\%$, $\pm 15\%$ and $\pm 20\%$ will be computed.

For D, the percent less than or equal to ± 5 mg/dL (± 0.28 mmol/L), ± 10 mg/dL (± 0.56 mmol/L), ± 12.0 mg/dL (± 0.67 mmol/L), ± 15 mg/dL (± 0.83 mmol/L), and ± 20 mg/dL (± 1.11 mmol/L) will be computed.

The *RD* and *D* distribution tables will be constructed using a threshold of 100 mg/dL(5.55 mmol/L).

As discussed in section 13.1 (Sample Size), with n = 240, the critical number (minimum) of accurate results is 228, which yields approximately 95% chance of satisfying the criterion if the actual probability that any result will be accurate is at least 96.77%. Symbolically, this criterion is equivalent to testing the hypothesis:

 $H_0: Prob\{accurate\} < 96.77\%$ versus the alternative:

 $H_1: Prob{accurate} \ge 96.77\%$

This test has a power of about 95%, with n =240, to reject H_0 if the actual probability of obtaining an accurate result is 96.77%. Conversely, there is about a 95% chance that the null will NOT be rejected if the actual probability that a result with the evaluation device would satisfy this definition of accuracy is only about 92.03%.

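### The power stated for the second primary criterion is wrong: a meter with 98.33% true accuracy passes the 236-of-240 rule about 63% of the time, not about 95%

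*Combined protocol and SAP*

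**What the plan says.** The primary objective (Section 7.1) has two parts, and this point concerns the second (7.1.2): at least 98% of results within ±15 mg/dL of the reference below 75 mg/dL, or within ±20% at or above it. Section 13.5.3 turns this into a count: "Thus, with n = 240, there must be at least 236 BGMS results satisfying this requirement". It sets the boundary between the null and alternative hypotheses at 98.33% and states the power: "There is approximately a 95% chance of rejecting H_0 in favor of H_1 if the actual probability that a meter measurement would satisfy" the limits ("mg/dL or 20% is 98.33"%). It adds that there is about a 95% chance of not rejecting if the probability that a result "would satisfy this definition of accuracy is only about 96.23"%.

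The first criterion is treated in the same way in Sections 13.1.3, 13.1.4 and 13.5.2. At least 228 of 240 results must be accurate, with about a 95% chance of passing at a true accuracy of 96.77% and about a 95% chance of failing at 92.03%. On the sample size, Section 13.1.1 says: "The sample size requirement is based on the primary objective, section 7.0".

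**The concern.** The accuracy at which the power is quoted equals the observed pass mark: 236/240 = 0.9833. When a meter's true accuracy equals the pass mark, the expected count of accurate results is the cut-off itself, so the chance of reaching it can be only a little above one half. For the first criterion the plan keeps the two quantities apart: the pass mark is 95% (228/240) and the accuracy needed for 95% power is 96.77%. In Section 13.5.3 they are the same number.

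The second criterion belongs to the primary objective, on which the sample size is said to rest, and the sentence in 13.5.3 is the plan's only statement of its power. A reader would conclude that a 98.33%-accurate meter carries about a 5% risk of failing. The text also allows the hypotheses to be adjusted if the final number of results is not 240, so the wrong figure would serve as the template for that adjustment.

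**Working it through.** **Inputs.** n = 240 results per system, from 120 samples in duplicate (Section 8.2). The cut-off is 236 for the second criterion (0.98 × 240 = 235.2, rounded up) and 228 for the first (0.95 × 240). The quoted accuracies are 96.77%, 92.03%, 98.33% and 96.23% (Sections 13.1 and 13.5).

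**Formula.** With p the true probability that a result is accurate, q = 1 − p, and results taken as independent:

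P(pass) = P(X ≥ c) = Σ C(240, k) q^k p^(240−k), summed over k = 0 to 240 − c inaccurate results.

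**Step 1: the plan's figures under this model.**

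| Criterion | Cut-off | True accuracy | Plan says | Exact binomial |
|---|---|---|---|---|
| First | 228 | 96.77% | pass about 95% | 95.03% |
| First | 228 | 92.03% | fail about 95% | 1 − 0.0503 = 94.97% |
| Second | 236 | 96.23% | fail about 95% | 1 − 0.0502 = 94.98% |
| Second | 236 | 98.33% | pass about 95% | **62.73%** |

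Three of the four reproduce, so this is the plan's own model. The fourth does not.

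**Step 2: the fourth figure in full.** At q = 0.0167 the expected number of inaccurate results is 240 × 0.0167 = 4.0, and at most 240 − 236 = 4 are allowed. The probabilities of 0, 1, 2, 3 and 4 inaccurate results are 0.0176, 0.0716, 0.1453, 0.1958 and 0.1970. Their sum is 0.627. With p = 236/240 unrounded it is 0.629. The failure risk is 1 − 0.627 = 0.373.

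**Step 3: the accuracy that gives 95%.** Solving P(X ≥ 236 | p) = 0.95 gives p = 0.99176, or about 99.18%. As a check, P(X ≥ 236 | 0.9918) = 0.951.

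**Step 4: other ways the 95% might have arisen, all at 98.33%.**

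| Variant | P(pass) |
|---|---|
| Normal approximation | 0.498 |
| Normal with continuity correction | 0.598 |
| Poisson | 0.627 |
| Cut-off 235 | 0.785 |
| Cut-off 234 | 0.890 |
| Cut-off 233 | 0.950 |
| 120 independent samples, cut-off 118 | 0.676 |

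Only a cut-off of 233 gives 95%. But 233/240 = 97.1%, which does not meet the 98% requirement and contradicts the stated 236.

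**Step 5: correlated duplicates.** Let the two results from a sample have correlation ρ, so that both are inaccurate with probability q² + ρpq. At 98.33% the pass chance is then 0.627, 0.625, 0.621, 0.621 and 0.676 for ρ = 0, 0.25, 0.5, 0.75 and 1.

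**Step 6: both criteria together.** The tolerances are nested: any result inside the tighter limits is also inside the wider ones. At 96.77% and 98.33%, each result falls inside the tight limits with probability 0.9677, between the two with probability 0.9833 − 0.9677 = 0.0156, or outside the wide limits with probability 0.0167. The chance of at most 4 results outside the wide limits and at most 12 outside the tight limits is 0.623. The second criterion alone gives 0.627, so it accounts for nearly all of the risk.

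**The case against.** The arithmetic cannot be rebutted. The case on the other side concerns consequence and scope.

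- **The decision rule does not depend on the wrong sentence.** The cut-off of 236 follows from the 98% requirement, and the figure that limits wrongly passing a poor meter (96.23%) reproduces. The error understates the risk that a good meter fails, which falls mainly on the sponsor. This stands: no acceptance decision changes.
- **The numbers that justify n = 240 in Section 13.1 are for the first criterion only, and they are right.** The plan states no joint power and does not say that it expects an accuracy of 98.33%. This also stands. The 37% failure risk applies at that accuracy; at about 99.2% or above, the 95% chance is met. Even so, 13.1.1 bases the sample size on the whole primary objective.
- **The error reaches beyond one sentence.** 98.33% is also the hypothesis boundary in 13.5.3, just as 96.77% is both boundary and 95%-power point in 13.5.2. Changing only the power sentence would leave the two sections built differently. This is right, and the fix must cover it. Quoting high power at the boundary itself is a wider matter of how both pairs of hypotheses are framed, and this correction does not settle it.
- **The replacement value depends on independence.** The duplicates share a sample, a meter and a strip lot. With fully correlated pairs (at least 118 of 120), a 95% chance needs about 99.32%, not 99.18%. This stands as a caveat and moves the requirement further from 98.33%.
- **A pass chance below one half at exactly 98% is not an error in itself.** It is 47.5%, and it follows from setting a cut-off on an observed proportion. The first criterion at exactly 95% gives 57.6%. This is accepted; the 47.5% is useful context only.

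**Conclusion.** The concern holds. With the 236-of-240 rule, a meter of 98.33% true accuracy passes 62.7% of the time. The stated figure of about 95% is too high by about 32 percentage points, and the failure risk is 37.3% rather than about 5%. The main figure assumes independent results, as the plan's own figures do; over the duplicate correlations examined it stays between about 62% and 68%.

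The documents do not show how the error arose. The pass mark 236/240 may have been entered where the 95%-power accuracy belonged, or 98.33% may have been worked out for a cut-off of 233. Either way the sentence is wrong as written, and it misstates the power of a primary criterion. The cut-off of 236, the sample size and the 96.23% figure are not affected.

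**What to change.** 1. **Section 13.5.3.** Choose one of two corrections. Either give about 99.18% as the true accuracy for 95% power and change the boundary in both hypotheses to the same value, so that the section follows 13.5.2; or keep 98.33% throughout and state the power there as about 63%.
2. **Section 13.1.** Beside the figures for the first criterion, add those for the second: cut-off 236, about 95% chance of passing at 99.18%, about 63% at 98.33%, and about 95% chance of failing at 96.23%. Add the joint chance of passing both criteria, which is about 62% at 96.77% and 98.33%.
3. **Assumption.** State that these figures treat the 240 duplicate results as independent. With fully correlated duplicates, a 95% chance on the second criterion needs about 99.32%.
4. **Final n other than 240.** Recompute the 95%-power accuracy from the actual cut-off; do not set it equal to the cut-off proportion.

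Keep n = 240 and the cut-off of 236. The cost is a correction of wording and figures, with no extra subjects, testing or procedures. The stated operating characteristic becomes less favourable, but it will be correct.

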13.6 Neonates < 24 hrs. old and Neonates in NICU – Other Objectives

In addition to the neonates less than 28 days of age, additional analyses of data from neonatal subjects ≤ 24 hrs. old and neonates in NICU will be performed.

- 13.6.1 Specifically, differences in BG results between BGMS and reference laboratory instrument will be plotted against the laboratory instrument results (modified Bland-Altman plot).
- 13.6.2 There must be at least 5 subjects <24 hrs. old and 5 subjects in NICU enrolled to perform this analysis. These groups may have any or all subjects in common.

13.7 Hematocrit Analysis – Other Objectives

Version: 140ct2022

- 13.7.1 Hematocrit will be measured for each subject. Mean, median, minimum, maximum, and standard deviation, will be computed for hematocrit determinations.
- 13.7.2 The effect of hematocrit on meter results will be presented via regression of differences between the meter and laboratory BG measurements against hematocrit.

13.8 Bilirubin Analysis – Other Objectives

For neonates who would have bilirubin results, regression analysis will be used to assess the effects of bilirubin on the difference between meter and laboratory reference method blood glucose measurements.

There must be at least 3 subjects enrolled with bilirubin recorded to perform this analysis. If fewer than 3, then the results will be reported in a table.

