5.0 Justification for the Design of the Clinical Study

Hypoglycemia is the most common metabolic disturbance occurring in the neonatal period, which can lead to neonatal morbidity and developmental sequelae. Screening at-risk infants and the management of low blood glucose levels in the first hours to days of life is a frequent issue in the care of newborn infant. Transitional neonatal hypoglycemia usually resolves within 2 or 3 days of age. Severe prolonged neonatal hypoglycemia can cause seizures, brain damage, and neurodevelopmental impairment. Signs of neonatal hypoglycemia are non-specific, and babies with hypoglycemia are frequently asymptomatic. Therefore, it is common to screen babies considered at high risk for neonatal hypoglycemia with repeated blood glucose measurements. Usually, plasma or serum samples are used for routine blood glucose estimation in a hospital laboratory. However, such an approach using a laboratory-based testing method is not practical in acute situations due to the delayed turnaround time. Therefore, BGMS are frequently used for the bedside estimation of blood glucose levels. Rapid measurement time, smaller volume of required blood samples, and enhanced usability are the main benefits of using BGMS compared with laboratory-based testing. Most BGMS that are currently used are initially developed for monitoring blood glucose levels in adult patients with diabetes. Neonatal blood differs from adult blood in two major aspects—it has lower concentrations of blood glucose and a wider range of hematocrit levels (Adamkin 2011; BAPM 2017; Harris et al 2012; Lucas et al 1988; Movalia and Ogino 2006; Nuntnarumit et al 2011; Roth-Kleiner et al 2010; Rozance 2006).

Protocol /CIP: GCA-PRO-2021-003-01 - Amendment 1

Version: 140ct2022

The CONTOUR NEXT and CONTOUR PLUS ELITE BGMSs are investigational BGMSs comprised of the blood glucose meter, the compatible test strips, and control solutions. They are automated systems intended for the quantitative measurement of glucose in neonatal blood, venous blood, fresh capillary whole blood drawn from the fingertip or palm. The system is intended to be used for self-testing by lay persons with diabetes and for near-patient testing by HCPs to monitor the effectiveness of diabetes control. Its use in this trial is for the quantitative measurement of glucose levels in neonates from fresh capillary whole blood drawn from the heel by HCPs in a clinical setting.

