7.0 Objectives and Hypotheses

Version: 140ct2022

The primary objective of the study is to evaluate the performance of CONTOUR NEXT and CONTOUR PLUS ELITE BGMSs with residual heel-stick capillary blood samples from neonates, i.e. babies who are less than 28 days old. The performance of the BGMS will be analyzed according to the following objectives:

- 7.1 **Primary Objective**: The accuracy criteria below are taken from CLSI. *Point-of-Care Blood* Glucose Testing in Acute and Chronic Care Facilities; Approved Guideline – Third Edition. CLSI document POCT12-A3. Wayne, PA: Clinical and Laboratory Standards Institute; 2013.
 - At least 95% of all blood glucose results shall fall within ±12.5% of reference values 7.1.1 (laboratory method) for glucose concentration ≥100 mg/dL (5.55 mmol/L) and within $\pm 12 \text{ mg/dL}$ ($\pm 0.67 \text{ mmol/L}$) at glucose concentrations < 100 mg/dL (5.55) mmol/L).
 - Note: Satisfying Criterion 7.1.1 would also satisfy the ISO 15917:2013 criteria of obtaining the $\pm 15\%$ of reference values (laboratory method) for glucose concentration $\geq 100 \text{ mg/dL}$ (5.55 mmol/L) and within $\pm 15 \text{ mg/dL}$ ($\pm 0.83 \text{ mmol/L}$) at glucose concentrations <100 mg/dL (5.55 mmol/L).
 - 7.1.2 At least 98% of values shall be within $\pm 20\%$ of reference values (laboratory method) for glucose concentration \geq 75 mg/dL (4.16 mmol/L) and within \pm 15 mg/dL (\pm 0.83 mmol/L) at glucose concentrations < 75 mg/dL (4.16 mmol/L).

Other Objectives: 7.2

- Evaluate the performance of both BGMSs for neonates who are <24 hours old. Compute differences between BGMS and laboratory blood glucose measurements and plot them against hematocrit results.
- Evaluate the performance of both BGMSs with blood samples from babies in the NICU.
- Compute differences between BGMS and laboratory blood glucose measurements and plot them against bilirubin results, for those subjects where bilirubin measurements were recorded (when available).

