11.4 Blood Glucose Testing

- 11.4.1 No blood will be taken from study subjects solely for this study. Neonatal blood will be collected for prescribed testing and residual blood from the sample will be used for this study. Blood will be collected following HCP's orders by nursing/phlebotomy staff using standard heel puncture techniques. All samples will be transported to the laboratory per standard practice and submitted for prescribed clinical testing. Samples will be collected according to hospital standards and procedures and will be collected into a tube containing anticoagulants (lithium heparin).
- 11.4.2 Neonatal blood samples will be inspected to verify if the volume drawn was sufficient to complete both prescribed clinical and investigational testing by laboratory personnel. Samples that do not have sufficient volume to complete the required investigational testing will not be used for the clinical trial.
- 11.4.3 If sufficient volume is available, this is the time of enrollment. No more than the agreed amount (50 uL) of capillary whole blood will be removed from the original sample to perform blood glucose testing on two investigational BGMSsand a hematocrit measurement.
- 11.4.4 The collected samples will be used within a maximum of 5 h of sample collection time, and will be kept at room temperature (23 \pm 5 °C) before evaluation.
- 11.4.5 Each blood sample for the study will be assigned an ID that is not traceable to the identity of the subject. The first digit will indicate the site ID followed by three digits indicating the sample ID as follows: X-001, X-002, X-003, and so on.
- 11.4.6 Strip lot (color code) will be determined via a randomization schedule provided by the Sponsor. The testing order of the meter will also be based on a randomization schedule. Note that one CONTOUR NEXT and one CONTOUR PLUS ELITE BGMS per subject will be used and the meters will be disinfected after use as per procedures listed in Appendix A.

11.4.7 For each subject, a CONTOUR NEXT BGMS, and a CONTOUR PLUS ELITE BGMS will be brought to the testing area. A test strip (as assigned for the given BGMS) will be inserted into each of the 2 meters (same color code strip lot for both meters).

- 11.4.8 A drop of blood will be placed on a piece of Parafilm (or other non-absorbent material) and immediately tested with the first and second meter.
- 11.4.9 The test strips in the two meters will then be replaced, to prepare the meters for duplicate testing.

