13.4 Weighted Least Squares Regression

Weighted least squares regressions of meter results against comparator results will be performed. If *M* represents the meter result, and *C* the comparator result, the linear model can be expressed as:

$$M = \beta_0 + \beta_1 C + \varepsilon$$
$$\varepsilon \sim N(0, cv * C)$$

The parameter *cv* is the coefficient of variation, which is assumed to be constant across the glucose range. The weighting function will be:

$$w = C^{-2}$$

This weighting function is used to account for the constant cv nature of glucose measurement (Draper and Smith, 1998).

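### Section 13.7.2 estimates the hematocrit effect without reference glucose as a covariate, so a calibration slope other than 1 would bias it if glucose and hematocrit are correlated

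*Combined protocol and SAP*

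**What the plan says.** Section 13.7.2 states: "The effect of hematocrit on meter results will be presented via regression of differences between the meter and laboratory BG measurements against hematocrit". It names no second regressor, no weights and no handling of the duplicates. It sets no significance level and no limit that the slope must meet. The matching objective in section 7.2 is graphical: "Compute differences between BGMS and laboratory blood glucose measurements and plot them against hematocrit results".

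Reference glucose enters other analyses, but never together with hematocrit. Section 13.4 says "Weighted least squares regressions of meter results against comparator results will be performed", with a free intercept and slope, weights C^-2, and a cv that "is the coefficient of variation, which is assumed to be constant across the glucose range". It has no hematocrit term. The modified Bland-Altman plots in 13.3 and 13.6.1 set differences against reference glucose only. No correlation between glucose and hematocrit is planned for reporting.

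Section 13.5.1 defines two metrics: a relative (percent) difference RD at or above the glucose threshold and, below it, "Difference (D) for reference result < threshold glucose", that is D = M − C. Section 13.7.2 does not say which one its differences are.

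Section 5.0 explains why hematocrit matters. Of neonatal compared with adult blood it says "it has lower concentrations of blood glucose and a wider range of hematocrit levels".

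**The concern.** Reference glucose is part of the difference, but it is not a covariate. Under the plan's own calibration model the difference still depends on reference glucose unless the slope is exactly 1. If babies with higher hematocrit tend to have lower or higher glucose in this sample, a regression on hematocrit alone credits part of that calibration error to hematocrit. Depending on sign, a meter with no hematocrit sensitivity could show some, or a real sensitivity could be partly cancelled.

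This is the plan's only quantitative look at one of the two features that section 5.0 gives as distinguishing neonatal blood, in a study meant to extend the intended use to neonates. At stake is how the hematocrit slope is read. The primary accuracy criteria in 7.1.1 and 7.1.2 do not depend on it.

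**Working it through.** The plan states no figure for this analysis, so there is none to reproduce.

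**Inputs from the documents.** The model M = b0 + b1·C + error (13.4); the difference regressed on hematocrit H (13.7.2); D and RD (13.5.1). On sample size, section 13.1.2 says: "There will be a minimum of N = 120 study samples entered into the study".

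**Assumed inputs (not in the documents).** SD(C) = 20 mg/dL; SD(H) = 7 points; b1 from 0.90 to 1.05; rho = corr(C, H) from −0.5 to 0; a hematocrit span of 40% to 65%, which is 25 points.

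**Step 1: bias when the difference is D.** Let g be the true hematocrit effect, so M = b0 + b1·C + g·H + e. Then

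M − C = b0 + (b1 − 1)·C + g·H + e.

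Regressing M − C on H alone estimates g + (b1 − 1)·rho·SD(C)/SD(H). The second term is the bias. For b1 = 1.05 and rho = −0.4 it is 0.05 × (−0.4) × 20/7 = −0.057 mg/dL per point, and 25 × (−0.057) ≈ −1.4 mg/dL.

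| b1 | rho | Bias per hematocrit point (mg/dL) | Bias, 40% to 65% (mg/dL) |
|---|---|---|---|
| 1.00 | any | 0 | 0 |
| any | 0 | 0 | 0 |
| 1.05 | −0.2 | −0.029 | −0.7 |
| 1.05 | −0.4 | −0.057 | −1.4 |
| 0.95 | −0.3 | +0.043 | +1.1 |
| 0.90 | −0.5 | +0.143 | +3.6 |

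The bias is proportional to SD(C): at 30 mg/dL each non-zero entry is 1.5 times as large. The last row is the outer end of the assumed range, not an expected case.

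**Step 2: bias when the difference is RD.** With g = 0, RD = 100·[(b1 − 1) + b0/C + e/C]. If b0 = 0, the calibration term is constant and does not load on H. If b0 is not zero, b0/C varies with glucose and the bias returns.

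**Step 3: simulation.** Settings: 120 samples, duplicates averaged, 2,000 runs per case, mean glucose 75 mg/dL, meter CV 5%, reference CV 1%, SDs as above.

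- b1 = 0.95, rho = −0.3, no true effect, intercept set so that the error is zero at the mean glucose: the mean slope of D on H was +0.042 (formula +0.043). With C added it was −0.002.
- Same calibration and correlation with a true slope of −0.15 mg/dL per point: the mean slope was −0.107 without C and −0.150 with C.
- About 99.5% of results in these two cases met the 12 mg/dL / 12.5% limits, so meeting the primary criterion does not exclude the bias.
- RD on H, b1 = 0.95, rho = −0.3, no true effect: rejection at an assumed two-sided 5% level was about 6% with b0 = 0 and 28% with the non-zero intercept.

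**Step 4: cost in precision.** Adding C inflates the standard error of the hematocrit coefficient by 1/√(1 − rho²) for a given residual variance: 1/√(1 − 0.16) = 1.09 at |rho| = 0.4 and 1/√(1 − 0.25) = 1.15 at 0.5.

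**The case against.** **No test is planned.** A reader might infer that the study runs a high risk of a false hematocrit finding. With a residual SD of 4 mg/dL, one point per sample and b1 = 1.05, a 5% test without C would reject in about 8%, 20% and 26% of trials at rho = −0.2, −0.4 and −0.5. But 13.7.2 only presents a regression. The documents support a statement about slope bias, not an error rate. For modest values that bias is small beside the ±12 mg/dL limit in 7.1.1.

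**The metric is open.** A reader might infer that any proportional calibration error would show up as hematocrit interference. That holds for D. Under RD, with a zero intercept, it does not. The objection stands to that extent, but RD does not protect against a non-zero intercept.

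**The correlation is undocumented.** Section 11.4.4 allows standing time ("The collected samples will be used within a maximum of 5 h of sample collection time"), and red cells consume glucose, so a reader might infer that storage creates a strong negative correlation. With SDs of 20 and 7, rho = −0.4 needs glucose to fall 0.4 × 20/7 = 1.14 mg/dL per hematocrit point. If consumption is proportional to hematocrit and mean hematocrit is 50% (both assumptions), the average loss would be about 57 mg/dL; rho = −0.2 would need about 29. Storage alone does not plausibly give rho near −0.4. Postnatal age is another possible route: section 5.0 says transitional hypoglycemia usually resolves within 2 or 3 days. That hematocrit also changes with age is an assumption.

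**Large calibration errors would often show elsewhere.** With b1 = 1.08, zero intercept, residual SD 4 and mean glucose 75, about 93% of results meet the primary limits, and the chance of at least 228 of 240 is about 12% if results are independent. An offsetting intercept removes this safeguard, as Step 3 shows. Section 13.4 also reports b1, so a reader can see one of the two conditions, but not the correlation.

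**Conclusion.** The point holds in a limited, conditional form. The regression in 13.7.2 omits reference glucose as a covariate, and no other planned analysis supplies the adjustment. If b1 differs from 1 and glucose and hematocrit are correlated, the slope for D is biased by (b1 − 1)·rho·SD(C)/SD(H); for RD, bias remains when the intercept is not zero. Under the assumed SDs with b1 = 1.05 and rho from −0.2 to −0.4, this is about −0.7 to −1.4 mg/dL from 40% to 65% hematocrit. The documents give none of these inputs, so the actual size is unknown and may be zero.

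A reader might go further and infer that the hematocrit result will be misleading, or that the accuracy claim is affected. The documents support neither. Both conditions for bias are unverified, the objective is descriptive with no acceptance limit, and the primary criteria do not use this regression. It is an inexpensive improvement to consider.

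**What to change.** In 13.7.2, for each BGMS, add hematocrit to the model of 13.4: M on C and hematocrit, with weights C^-2, and with duplicates averaged or clustered by sample. Report the hematocrit coefficient with its 95% interval, and report the glucose-hematocrit correlation. With the same weights, regressing M − C on C and hematocrit gives the same hematocrit coefficient, because subtracting C only lowers the coefficient of C by 1. Keep the plot of differences against hematocrit from 7.2 as the unadjusted display, and state whether D or RD is plotted.

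No new data are needed: section 13.10 already makes a sample non-evaluable without a valid hematocrit and a valid Cobas value. The cost is a wording change, one degree of freedom, and a standard error about 9% to 15% larger if the correlation is 0.4 to 0.5 in size.
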